2. OBJECTIVE(S) AND ENDPOINT(S)

Objective(s)	Endpoint(s)
Primary	
Assessment of the cutaneous and ocular tolerance of two cosmetic facial cleansers after 21 (+ 2) days of product use per the intended instructions in healthy female subjects with clinically assessed sensitive skin.	Dermatologist and ophthalmologist visual assessment of cutaneous and ocular irritation after 21 (+ 2) days of test product use.
Secondary	
Assessment of the cutaneous and ocular tolerance of two cosmetic facial cleansers after 21 (+ 2) days of product use per the intended instructions in healthy female subjects with clinically assessed sensitive skin.	Subject self-assessment question responses (redness, dryness, burning, itching and stinging) with regards to product use experience on the face and around the eyes after 21 (+ 2) days of test product use.
To evaluate the general safety of two cosmetic facial cleansers.	Frequency and severity of Adverse Events

3. STUDY PLAN

3.1. Study Design

Overall Design

This is an assessor blind (dermatologist and ophthalmologist) clinical in use study to determine the local cutaneous and ocular tolerance of two cosmetic facial cleanser products when used as per the intended instructions for use in a population of healthy female subjects with clinically assessed sensitive skin.
 
Subjects who have sensitive skin as classified by a positive reaction to a lactic acid Stinging Test will be asked to use one of two cleansing products as part of their normal skin care routine for 3 weeks.
 
Both test products are the same formulation but are differentiated by the dispensing pack; to either a micellar cleanser or a foaming cleanser.
 
Subjects will be instructed to cleanse their face with one of the two test products at home twice-daily, for 21 (+ 2) days, including a supervised first application at the study site (Visit 2) and a final application at home on the morning of the final visit (Visit 3), as per the intended instructions for use.

 GlaxoSmithKline	Document Name	Clinical Protocol 207782		
	Type	Version	Document Identifier	Effective Date
	eldo_clinical_doc	2.0; Most-Recent; Effective; CURRENT	090032d580d48db0	26-May-2017 05:53:15
	Reason For Issue	Auto Issue		

A qualified dermatologist and a qualified ophthalmologist will assess the baseline cutaneous and ocular irritation of prospective subjects at Visit 2. For a subject to be considered eligible to participate in the study, all dermatologist and ophthalmologist assessment scores must be zero. Further dermatologist and ophthalmologist assessments will be completed 1-hour (\pm 20 minutes) post supervised first product use and at the final visit (Visit 3) at the end of the 21 (+2) day product use period. The intensity of any visual signs of cutaneous and ocular irritation will be recorded by the dermatologist and ophthalmologist, according to the assessment scales detailed in Appendix 3 and 4.

The dermatologist will also determine each subject's facial skin type as dry, oily or normal/combination skin. Any subject classified as having oily skin will not be considered eligible for participation in the study as they do not represent the target population for the product.

Subjects will be asked to complete self-assessment questions at Visit 2 prior to any study product use. In addition, randomized subjects will be asked to complete the self-assessment questions 1 hour (\pm 20 minutes) post supervised first product use and at the end of the 21 (+2) day product use period.

The objective of this clinical study is to assess the cutaneous and ocular local tolerance of two cosmetic facial cleansers in healthy females with sensitive skin under normal conditions of use.

Visit 1 – Screening Visit

The following assessments will be conducted:

1. Subject Informed Consent taken
2. Subject demographics collected
3. Medical history details collected
4. Details of current and concomitant medication collected
5. Inclusion/Exclusion criteria
6. Contact lens wearer status assessment (Yes or No)
7. Clinical diagnosis of sensitive skin confirmed by Lactic Acid sting test
8. Determination of subject eligibility to participate in the study
9. Adverse events will be reported following the Lactic Acid stinging test procedure

Visit 2 – Baseline Visit

Within 7 days of the Screening Visit

The following assessments will be conducted:

1. Current/Concomitant medications review
2. **INCLUSION/EXCLUSION CRITERIA**

 GlaxoSmithKline	Document Name	Clinical Protocol 207782		
	Type	Version	Document Identifier	Effective Date
	eldo_clinical_doc	2.0; Most-Recent; Effective; CURRENT	090032d580d48db0	26-May-2017 05:53:15
	Reason For Issue	Auto Issue		

3. Fitzpatrick skin type assessment (Appendix 2)
4. Dermatologist assessment of skin type status (dry, oily or normal/combination)
Inclusion criteria 5e and Exclusion criteria 7f
5. Clinical dermatologist assessment for eligibility to participate in the study (including visual examinations) (Appendix 3). Inclusion criteria 5c
Note: subject must have a total score of zero for inclusion into the study
6. Clinical ophthalmologist assessment for eligibility to participate in the study (including visual examinations) (Appendix 4). Inclusion criteria 5d
Note: subject must have a total score of zero for inclusion into the study.
7. Subject self-assessment questions (Appendix 5). Prior to product use.
8. Continued eligibility check
9. Randomization and stratification
10. Dispense assigned study product and diary card/instructions for use
11. Supervised first use of assigned product
12. Dermatologist (Appendix 3) and ophthalmologist (Appendix 4) assessments 1 hour (\pm 20 minutes) post supervised first product application
13. Subject self-assessment questions (Appendix 5) 1 hour (\pm 20 minutes) post first supervised use
14. Adverse events assessment.

Visit 3 - Week 3 / Exit from Study (21 (+ 2) Days)

The following assessments will be conducted:

1. Current/Concomitant medications review
2. Continued eligibility check
3. Return study product and diary card/instructions for use
4. Diary card check to confirm compliant product use
5. Dermatologist final assessment of tolerance (Appendix 3)
6. Ophthalmologist final assessment of tolerance (Appendix 4)
7. Subject final self-assessment questions (Appendix 5)
- ~~8. Return assigned cleanser and Diary Card/Instructions for use~~
9. Adverse event assessment
10. Subject discharge from the study site following completion of all study procedures

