6.2.9. Supervised Product Application

Each eligible subject will be randomised to a strata based on contact lens wearer status (Yes or No) and cosmetic skin type (dry or Normal/Combination) to receive one of the two cleansing products under investigation and given instructions on how to apply the product. Sufficient product will be provided so that the product can be used for the complete study period.

The first use of the assigned product will be performed at the study site, under study site staff supervision. One hour (+20 minutes) after the first product application subjects will undergo further dermatologist (per section 6.2.5) and ophthalmologist (per section 6.2.6) assessments and be asked to respond to the subject self-assessment questions (Appendix 5).

If subject is a contact lens wearer, contact lenses should be removed prior to any product application.

Subjects will receive a diary card with their assigned product to be completed at home to record product use. Subjects will use the product at home, twice a day during the study period of 21 (+ 2) days, and will be instructed to contact the study site if they have any reactions.

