6.3. Visit 3 - Last Subject Last Visit (LSLV) and Study Conclusion

Subjects will return to the study site after 21 (+ 2) days of twice daily product use. Subjects will return their test products and diary card. The diary card will be reviewed to check compliance and evaluate subject comments. The total number of product applications and total number of missed product applications will be recorded in the CRF.

Final dermatologist (per section 6.2.5) and ophthalmologist (per section 6.2.6) assessments will be completed and the subject will answer the self-assessment questions (Appendix 5) based on their experience of using the product.

 GlaxoSmithKline	Document Name	Clinical Protocol 207782		
	Type	Version	Document Identifier	Effective Date
	eldo_clinical_doc	2.0; Most-Recent; Effective; CURRENT	090032d580d48db0	26-May-2017 05:53:15
	Reason For Issue	Auto Issue		

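### Subjects' symptom answers could be coloured by the clinician examinations: the visit lists put the questions afterwards, and no visible text fixes the order or bars comment first

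*Protocol*

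**What the plan says.** Protocol 3.1 gives numbered activity lists for each visit; the synopsis and SAP 1.1 repeat them.

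- Visit 2, before product: the dermatologist examination is item 5, then "6. Clinical ophthalmologist assessment for eligibility to participate in the study", then "7. Subject self-assessment questions (Appendix 5). Prior to product use".
- Visit 2, after the supervised application: "12. Dermatologist (Appendix 3) and ophthalmologist (Appendix 4) assessments 1 hour" is followed by "13. Subject self-assessment questions (Appendix 5) 1 hour".
- Visit 3: the dermatologist is item 5, then "6. Ophthalmologist final assessment of tolerance (Appendix 4"), then "7. Subject final self-assessment questions (Appendix 5").

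The procedure text runs the same way. In 6.2.9 the subject undergoes further dermatologist and ophthalmologist "assessments and be asked to respond to the subject self-assessment questions (Appendix 5"). In 6.3 the final clinician "assessments will be completed and the subject will answer the self-assessment questions (Appendix 5) based on their experience of using the product".

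Protocol 9.3.3 makes the five self-assessed symptoms secondary endpoints. SAP 4.5.1 presents them at each time point, separately for eyes and face, with a sum over the post-baseline observations. Protocol 5.3.2 keeps the two clinicians blind to product assignment and says nothing about what they may tell the subject.

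**The concern.** Section 1 of the protocol describes sensitive skin as a sensory reaction (stinging, burning, itching) without visible change. By that account the visual gradings can miss the reaction this population was selected for. The self-assessment is the only planned, scored questioning about those sensations after product use; otherwise they would surface only through diary comments or adverse event reports. It adds most when it is independent of the clinicians' reading.

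A subject asked about redness or dryness straight after a dermatologist has inspected her face may answer partly from that encounter. A reassuring remark could lower what she reports, and attention drawn to a sign could raise it. The study is non-comparative (Protocol 3.4), so its product is the symptom frequency in each arm, and a shift common to both arms does not cancel out of that figure.

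**Working it through.** No sample size, power or error rate is involved, so the check sets the passages side by side.

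**1. Listed order (Protocol 3.1).**

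| Time point | Examinations | Self-assessment |
|---|---|---|
| Visit 2, before product | items 5 and 6 | item 7 |
| Visit 2, 1 hour | item 12 | item 13 |
| Visit 3 | items 5 and 6 | item 7 |

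The questions come second at 3 of 3 time points. The synopsis and SAP 1.1 carry the same item numbers, so each also gives 3 of 3. Sections 6.2.9 (1 hour) and 6.3 (Visit 3) name the examinations first. No visible passage puts the questions first.

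**2. Is the order binding?** Section 6 sends the reader to the Schedule of Events for exact timing. The Schedule assigns procedures to visits. Its footnotes b to d give the examinations and the questions the same 1-hour (± 20 minutes) window, and footnote d requires the baseline questions before first application. It sets no order between examination and questions. Section 6.2.7 likewise fixes the questions relative to product use, not relative to the examinations. The lists therefore suggest an order without any sentence imposing it.

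**3. Is there a safeguard?** Section 5.3.2 concerns product assignment. Sections 6.2.5 and 6.2.6 make each clinician's grading final but do not address disclosure. Section 8.4 covers handling of subject-reported data, not the conditions under which they are given. None requires findings to be withheld until the subject has answered.

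**4. What is exposed?** Items per time point: 5 symptoms × 2 sites (face, eyes) = 10. Over three time points: 10 × 3 = 30 answers per subject, of which 10 × 2 = 20 follow product use. This counts answers given under the listed order, not answers shown to be wrong.

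**5. What is not exposed?** Protocol 9.2.3 and SAP 4.4.1.1 define success as more than 50% of subjects per arm with combined clinician scores of zero at Day 21 (+2). Self-assessment does not enter that criterion.

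**6. Does the shared baseline order remove the problem?** Only if results were expressed as change from baseline. SAP 4.5.1 tabulates each time point and a post-baseline sum, so any effect of the order stays in the reported frequencies.

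**The case against.** The strongest reply is that list position is not a mandated sequence. The lists are not strictly chronological: at Visit 1 the eligibility criteria are item 5 although the lactic acid test they depend on is item 7, and at Visit 2 they are item 2 although the criteria checked there rest on items 3 to 6. A site could ask the questions first at 1 hour without breaching an explicit rule. This stands, and it limits the claim to order as listed. It does not remove the need for a rule: if the lists govern, the questions come second; if they do not, the order is uncontrolled and may vary between subjects.

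A second reply is that questions first could prompt the subject to voice symptoms to the assessors, whose gradings are the primary endpoint. That is a real trade-off. It is met by keeping her answers and symptoms from them until the scores are recorded.

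Third, Appendix 5 is not in the text available here. The amendment log shows that it carries timing information, so a safeguard there cannot be excluded.

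Three stronger readings might be inferred, and the documents do not support them:

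- *The examinations cause the symptoms.* Sections 6.2.5 and 6.2.6 describe visual inspection and observation; no instilled agent or contact procedure is mentioned.
- *Clinicians tell subjects their findings.* Nothing says so; the visible text only fails to prevent it.
- *The comparison of arms or the success criterion is biased.* The listed order is the same in both arms, the assessors are blind to product, no formal inference is planned, and success rests on clinician scores. That subjects can recognise their own product is a separate feature of an assessor-blind design and does not bear on order.

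**Conclusion.** The point holds as a modest weakness in the conduct of a descriptive secondary endpoint. The order is confirmed at all three time points, no visible text controls it or bars comment, and the subjects' answers could be coloured as a result. Neither the size nor the direction of any effect can be derived from the documents.

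The conclusion assumes that sites follow the lists as printed, or at least are not told otherwise, and that Appendix 5 contains no instruction on order or disclosure. If it does contain one, the remaining task is to bring the lists and procedure text into line with it. This is a worthwhile improvement and not a threat to the study's main conclusion.

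**What to change.** In the synopsis, Protocol 3.1, 6.2.7, 6.2.9 and 6.3, and SAP 1.1, renumber the lists where needed and state that:

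1. the subject completes Appendix 5 before the dermatologist and ophthalmologist examine her at baseline, at 1 hour (within the existing window) and at Visit 3;
2. the clinicians do not discuss findings with her until she has done so;
3. her answers are not shown to the assessors, and her symptoms are not discussed with them, until their scores are recorded.

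The cost is a wording change and brief staff instruction, with no added visit or procedure. There are two small downsides. At baseline, some subjects who then fail the examinations will already have answered the questions. Staff must also keep subjects from volunteering symptoms before grading. The SAP addendum describes itself as written after unblinding, so if the study ran on the current wording, the remaining step for this trial is to state in the report which order the site used.

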3.2. Subject Restrictions

Lifestyle/ Dietary

During the entire study (Screening – Last Subject Last Visit (LSLV)) the following should be avoided:

 GlaxoSmithKline	Document Name	Clinical Protocol 207782		
	Type	Version	Document Identifier	Effective Date
	eldo_clinical_doc	2.0; Most-Recent; Effective; CURRENT	090032d580d48db0	26-May-2017 05:53:15
	Reason For Issue	Auto Issue		

1. Changing any cosmetic habits, including personal hygiene.
2. Addition of any new cosmetic product to their current regimen or switching brands of facial cosmetic products.
3. Changing dietary habits.
4. Exposure to artificial ultraviolet (UV) light or cosmetic procedures (includes tanning beds, Intense Pulsed Light, etc.) on the face for the duration of the study.
5. Introduction of new products during the study, including but not limited to soap, laundry detergent, or fabric softener.
6. If subject is a contact lens wearer, contact lenses should be removed prior to product application.

Baseline Visit (Visit 2):

1. Application of any leave-on cosmetics (e.g. creams, lotions, foundation, mascara, eyeliner and concealer) to the face prior to the Baseline Visit (Visit 2) should be avoided on the day of the visit.

Final Visit (Visit 3):

2. Application of any leave-on cosmetics (e.g. creams, lotions, foundation, mascara, eyeliner and concealer) to the face should be avoided on the day of the visit.
3. Application of any detergents (e.g. soaps, shampoos, and bath and shower products) to the face, other than the dispensed test product should be avoided on the day of the visit.

Medications and Treatments

During the entire study (Screening – LSLV) the following medications and treatments should be avoided:

1. Aesthetic, cosmetic or dermatological treatment of the face and/or eyes
2. Change in hormone treatment or contraception

 GlaxoSmithKline	Document Name	Clinical Protocol 207782		
	Type	Version	Document Identifier	Effective Date
	eldo_clinical_doc	2.0; Most-Recent; Effective; CURRENT	090032d580d48db0	26-May-2017 05:53:15
	Reason For Issue	Auto Issue		

3. Use of the following medications:

- a. Systemic or topical corticosteroids
- b. Systemic or topical immunosuppressive drugs
- c. Systemic or topical antihistamines, Vitamin A acid and its derivatives, or non-steroidal anti-inflammatory drugs
- d. Concomitant topical treatment of the face and or eyes

3.3. Type and Planned Number of Subjects

Healthy female subjects, aged 18 to 65 years with sensitive skin and no dermatological or ophthalmological disorders will be enrolled into this study. Female subjects with sensitive skin have been selected as they are the target consumers for the finished product with greater familiarization and habitual use of facial cleanser products. Prospective subjects shall be frequent users of make-up, including eye make-up.

Subjects with sensitive skin as determined by a positive response to the lactic acid Stinging Test will be considered eligible to participate into the study. Subjects with a Fitzpatrick phototype I to IV will be recruited to ensure any reactions are clearly visible on subject's skin. In addition to subjects who have a positive response to the lactic acid Stinging test, eligible subjects will have skin type assessed by a qualified dermatologist, and only subjects with dry or normal/combination skin will be considered eligible to participate in the study. Subjects with oily skin will not be enrolled as they do not represent the target population for the test products.

A sufficient number of subjects will be screened (up to 170) to randomize at least 92 subjects (46 per treatment group) to ensure that at least 40 subjects in each treatment group complete the study (80 subjects in total).

Randomization will be stratified by both contact lens wearer status (yes or no) and skin type (dry or normal/combination) to ensure that an equal population of contact lens wearers and skin type (dry or normal/combination) randomized to each treatment.

The sample size is based on clinical considerations to provide descriptive information on the local tolerance and safety of the test products and is consistent with ANVISA guidelines (ANVISA, 2012).

 GlaxoSmithKline	Document Name	Clinical Protocol 207782		
	Type	Version	Document Identifier	Effective Date
	eldo_clinical_doc	2.0; Most-Recent; Effective; CURRENT	090032d580d48db0	26-May-2017 05:53:15
	Reason For Issue	Auto Issue		

3.4. Study Design and Application Amount Justification

This is a single center, 2-arm, parallel group, non-comparative, assessor (dermatologist and ophthalmologist) blinded study in healthy female subjects with clinically assessed sensitive skin, conducted under the supervision of a dermatologist and ophthalmologist, to assess the cutaneous and ocular local tolerance of two cosmetic facial cleansers when used for a period of 21 (+2) days as per the intended instructions for use.

A lactic acid stinging test will be used to confirm whether a subject has sensitive skin (see 6.1.7). A subject must have a lactic acid stinging response **COMBINED** score of at least 2 (combined from each time point assessment) to be considered to have sensitive skin and therefore be eligible to participate in the study. A trained technician will conduct the lactic acid Stinging Test on subjects to ascertain whether a subject has sensitive skin.

Eligible subjects will be randomized and stratified, based on contact lens wearing status and skin type, to receive one of the two facial cleansing products under investigation and given instructions on how to correctly apply the product. Sufficient product will be provided so that the product can be used twice daily for the complete duration of study period.

The first use of the assigned test product will be performed at the study site, under study site staff supervision. One hour (± 20 minutes) after the first product application subjects will have further dermatologist and ophthalmological evaluations and the subject self-assessment questions will be asked a second time. Subjects will receive a diary card to record twice daily product use over the duration of the study. Subjects will be instructed to use the test product twice daily at home during the study period of 21 (+2) days and will be instructed to contact the study site if they have any reactions.

At the end of the study period, final dermatological and ophthalmological assessments will be performed on all subjects. Subjects will also be asked the self-assessment questions based on their experience of product use.

Subjects will return their completed diary and all of the product packages, whether empty or not. The diary will be verified for adequate completion.

Assessments:

A qualified dermatologist and a qualified ophthalmologist will assess subjects at Visit 2 to determine eligibility prior to any study product use, and 1 hour (± 20 minutes) following first supervised test product use. This is to ensure that the subject is free of any preexisting dermatological and ophthalmological pathology prior to using the study products (Edward,

 GlaxoSmithKline	Document Name	Clinical Protocol 207782		
	Type	Version	Document Identifier	Effective Date
	eldo_clinical_doc	2.0; Most-Recent; Effective; CURRENT	090032d580d48db0	26-May-2017 05:53:15
	Reason For Issue	Auto Issue		

2008). Additionally, a final assessment at Visit 3 will be completed at the end of the 21 (+2) day product use period.

The intensity of any visual signs of cutaneous or ocular irritation will be recorded by the dermatologist and ophthalmologist, according to the severity of the reactions (Appendix 3 and 4). The dermatologist and ophthalmologist are responsible for grading the reactions, and their opinion on the classification of the irritation scores is final.

Female subjects with a Fitzpatrick phototype I to IV will be recruited to ensure any reactions are clearly visible on their skin.

Each subject's medical history and medication history will be reviewed, as well as inclusion/exclusion criteria. Site staff will review lifestyle guidelines and product directions with eligible subjects.

A dermatologist will characterize each subject's skin and subjects with dry or normal/combo skin type who meet all other inclusion and exclusion will be included in the study. Subjects with oily skin will be excluded from the study.

Subjects will be asked to answer a series of self-assessment questions prior to any product application (Appendix 5).

Any skin irritation will be assessed by a dermatologist in the product application area and periocular area using the criteria recommended by the US Department of Health and Human Services Food and Drug Administration (FDA), 1999. The intensity of the reactions will be classified according to the scores obtained in the applied scale, according to Appendix 3.

Any ocular irritation will be assessed by an ophthalmologist, through the observation of the presence of two factors: Lacrimation Intensity and Conjunctiva Involvement, according to Appendix 4. For the initial pre-treatment assessment, the 1 hour after the first application assessment, and for the final day 21 (+2) day assessment, each response will be graded as per the ocular reaction intensity classification scale (Appendix 4).

Application Quantity:

The application quantity of the study products has been selected based on the assumption that, typically, 4ml of a cleansing product will be applied to a facial area of approximately 400cm², as consistent with the average amount of non-lathering cleanser reported in the literature (Loretz, 2008).

 GlaxoSmithKline	Document Name	Clinical Protocol 207782		
	Type	Version	Document Identifier	Effective Date
	eldo_clinical_doc	2.0; Most-Recent; Effective; CURRENT	090032d580d48db0	26-May-2017 05:53:15
	Reason For Issue	Auto Issue		

Both test products are the same formulation but are differentiated by the dispensing pack; to either a micellar cleanser or a foaming cleanser.

Micellar Cleanser instructions for use: Use morning and evening. Apply to a cotton pad and wipe over the entire face and closed eyes to gently cleanse. No need to rub or rinse. Cotton pads will be supplied.

Micellar Foaming Cleanser instructions for use: Use morning and evening. Massage gently onto wet skin on the face using fingertips, rinse thoroughly and pat skin dry.

